7.1.1 Pre-randomization Period - On admission prior to study treatment administration

The study will be explained to the parents of a potentially eligible neonate prior to birth, if possible, giving the parents the maximum time to make an informed choice. Once parental/maternal written informed consent has been obtained either prior to or after birth, the neonate's eligibility to take part in the study will be assessed according to the post-birth inclusion and exclusion criteria. If the neonate becomes eligible, then the medical history of the mother, the complications during pregnancy and the prenatal use of corticosteroids will be collected.

If the neonate becomes eligible, then the following information will be collected:

- Birth weight, occipital-frontal circumference (OFC), length;
- Apgar score at 1 and 5 min from birth;
- All medical conditions diagnosed before treatment drug administration, to be reported as "Medical History". To this group should be added thereafter those congenital conditions that, even if already present at birth, could be diagnosed after study treatment administration (including: major organ malformations, genetic diseases and/or chromosomal abnormalities);
- Concomitant medications;
- Clinical signs of RDS, such as tachypnea, retractions, nasal flaring, expiratory grunt;
- SpO₂ along with vital signs (systolic, diastolic and mean blood pressure, heart rate, respiratory rate);

- Fraction of inspired oxygen (FiO_2);
- Type of respiratory support (CPAP, BiPAP, NIPPV);
- Blood gas analysis (values of pH, pCO_2 , pO_2 , HCO_3 , BE, lactate), when feasible.

7.1.2 Day 1 - From study treatment administration to 24 hours post-treatment

Once the neonate's eligibility to take part in the study is confirmed, the Investigator will have to call/check the IRT to randomize the neonate to the treatment group (LISA or ETT).

Before starting the procedure:

Within 15 minutes before starting the procedure (before laryngoscope insertion), the following information will be collected:

- SpO_2 along with vital signs (systolic, diastolic and mean blood pressure, heart rate, respiratory rate);
- Fraction of inspired oxygen (FiO_2);
- Type of respiratory support (CPAP, BiPAP, NIPPV);
- Non-invasive ventilation parameters (CPAP pressure, BiPAP pressures, NIPPV peak pressure, PEEP, mean airway pressure);
- Pain score assessment (PIPP score) [26] by observing the subject for 15 seconds (see [APPENDIX IV](#));
- Blood gas analysis (values of pH, pCO_2 , pO_2 , HCO_3 , BE, lactate), unless the time from the blood gas analysis at screening is less than 1 hour. In this case only one blood gas analysis is acceptable;
- All medical conditions diagnosed before treatment drug administration, to be reported as "Medical History", including congenital conditions that could be diagnosed after study treatment administration;
- Concomitant Medications.

After Starting the Procedure:

From the start of the procedure (laryngoscope insertion) through the first 24 hours from administration, the following information will be collected:

- SpO_2 and FiO_2 at time 0 (end of surfactant administration), and at 5, 15, 30 min, 1 hour, 6, 12 and 24 hours after the end of study treatment administration;
- Vital signs (SDB, DBP, MBP, HR, RR): 15, 30 min, 1 hour, 6, 12 and 24 hours after the end of study treatment administration; HR and RR to be reported also at time 0 and 5 min (as showed in flow chart [Table 2](#));
- Evaluation of respiratory support: any change in non-invasive ventilation, need for intubation and invasive mechanical ventilation with the relevant dates and times;
- If applicable, NIV parameters (as specified above) at 30 minutes, 1 hour, 6, 12 and 24

- hours after the end of treatment administration;
- Evaluation of oxygen alone use: duration of needing supplementary oxygen with the relevant dates and times;
- PIPP score immediately following surfactant administration after observing the neonates for 30 seconds (see [APPENDIX IV](#));
- Capillary or arterial blood gas analysis (values of pH, pCO₂, pO₂, HCO₃, BE, lactate) at 1 hour, 6 hours and 24 hours after the end of study treatment administration;
- Surfactant- and procedure-related adverse events will be strictly monitored during the whole procedure for surfactant administration (see section [10.8](#));
- Adverse events diagnosed after treatment administration (including worsening of conditions pre-existing to treatment); major complications of prematurity (listed in [APPENDIX III](#)) to be recorded among adverse events;
- Further neonatal concomitant medications.

7.1.3 48 hrs after study treatment administration

The following information will be collected:

- FiO₂, SpO₂, vital signs (SBP, DBP, MBP, HR and RR) and, if applicable, NIV parameters (as specified above) at the same time;
- Evaluation of respiratory support: any change in non-invasive ventilation, need for intubation and invasive mechanical ventilation with the relevant dates and times;
- Evaluation of oxygen alone use: duration of needing supplementary oxygen with the relevant dates and times;
- Blood gas analysis (values of pH, pCO₂, pO₂, HCO₃, BE, lactate);
- Further neonatal concomitant medications and adverse events (including worsening of conditions pre-existing to treatment), as well as changes in those already reported; major complications of prematurity (listed in [APPENDIX III](#)) to be recorded among adverse events.

7.1.4 72 hrs after study treatment administration

The following information will be collected:

- FiO₂, SpO₂, vital signs (SBP, DBP, MBP, HR and RR) and, if applicable, NIV parameters (as specified above) at the same time;
- Evaluation of respiratory support: any change in non-invasive ventilation, need for intubation and invasive mechanical ventilation with the relevant dates and times;
- Evaluation of oxygen alone use: duration of needing supplementary oxygen with the relevant dates and times;
- Blood gas analysis (values of pH, pCO₂, pO₂, HCO₃, BE, lactate);

- Further neonatal concomitant medications and adverse events (including worsening of conditions pre-existing to treatment) as well as changes in those already reported; major complications of prematurity (listed in [APPENDIX III](#)) to be recorded among adverse events.

7.1.5 120 hrs after study treatment administration

The following information will be collected:

- FiO₂, SpO₂ and vital signs (SBP, DBP, MBP, HR and RR) at the same time;
- Evaluation of respiratory support: any change in non-invasive ventilation, need for intubation and invasive mechanical ventilation with the relevant dates and times;
- Evaluation of oxygen alone use: duration of needing supplementary oxygen with the relevant dates and times;
- Further neonatal concomitant medications and adverse events (including worsening of conditions pre-existing to treatment) as well as changes in those already reported; major complications of prematurity (listed in [APPENDIX III](#)) to be recorded among adverse events.

7.1.6 28 days PNA

The following information will be collected:

- FiO₂ (highest recorded value), SpO₂, HR and RR at the same time;
- Evaluation of respiratory support: any change in non-invasive ventilation, need for intubation and invasive mechanical ventilation with the relevant dates and times;
- Evaluation of oxygen alone use: duration of needing supplementary oxygen with the relevant dates and times;
- Further neonatal concomitant medications and adverse events (including worsening of conditions pre-existing to treatment) as well as changes in those already reported; major complications of prematurity (listed in [APPENDIX III](#)) to be recorded among adverse events.

In case the neonate was discharged home (either by the recruiting site or by a continuing care site) prior to 28 days of life, the neonate should be recalled for an on-site clinic visit at the recruiting site. If not feasible, any effort should be made to collect information about the occurrence of any adverse events as well as about any change in concomitant medications. The Investigator should contact the family pediatrician to collect the relevant information.

In case the treated neonate was transferred to a continuing care site prior to 28 days PNA and the neonate is still hospitalized there, the neonate should be recalled at the recruiting site for the visit. If this is not feasible, the visit can be replaced by a contact/phone call by the Investigator to the physician of the continuing care site to collect relevant information and check the occurrence of any other adverse event as well as of any change in concomitant medications.

7.1.7 36 weeks PMA

The following information will be collected:

- Weight
- FiO₂ (highest recorded value) SpO₂, HR and RR at the same time;
- Evaluation of respiratory support: any change in non-invasive respiratory support, need for intubation and invasive mechanical ventilation with the relevant dates and times;
- Evaluation of oxygen use alone: duration of needing supplementary oxygen with the relevant dates and times;
- If receiving respiratory support via nasal cannulae: evaluation if flow rate ≤ 2 l/min or > 2 l/min
- BPD assessment: breathing room air or on oxygen, if neonate has received oxygen for at least 28 days, need of positive-pressure respiratory support (see Section [7.2.3](#));
- Further neonatal concomitant medications and adverse events (including worsening of conditions pre-existing to treatment) as well as changes in those already reported; major complications of prematurity (listed in [APPENDIX III](#)) to be recorded among adverse events.

In case the subject is discharged home or transferred to a continuing care site prior to this visit, the subject should be recalled as soon as possible for an on-site clinic visit at the recruiting site. If not feasible, any effort should be made to collect relevant information for BPD assessment, adverse events as well as any change in concomitant medications. The investigator should therefore contact the physician of the continuing care site or the family pediatrician to collect the relevant information. In case study visits or procedures are modified or missed due to COVID-19, the relevant information will be recorded in the eCRF. If the subject was discharged without any supplemental oxygen or respiratory support, an on-site visit is not mandatory, but the Investigator should contact the family pediatrician to collect the relevant information to complete BPD evaluation.

7.1.8 Discharge home or 40 weeks PMA (whichever comes first)

The below assessments will be performed at discharge, or at 40 weeks PMA if the infant is still in hospital. The following information will be collected:

- SpO₂, HR and RR at the same time;
- Weight, OFC and length;
- Evaluation of respiratory support (if present): non-invasive respiratory support, or invasive mechanical ventilation and related FiO₂;
- If receiving respiratory support via nasal cannulae: evaluation if flow rate ≤ 2 l/min or > 2 l/min
- Evaluation of feeding status, hearing screen status, medications for respiratory problems;

- Assessment of relevant neonatal co-morbidities, their severity and treatment;
- Further neonatal concomitant medications and adverse events (including worsening of conditions pre-existing to treatment) as well as changes in those already reported.

In case the infant had been transferred to a continuing care site, the recruiting site is responsible for the proper continuation of data collection and documentation of the primary and secondary outcomes. The investigator of the recruiting site should keep contacts and provide the continuing care site with written instruction about management of the above as well as for the reporting of serious AE, if any. The recruiting site should receive a discharge letter clarifying as much detailed information as possible the progress in subject's conditions.

Routine clinical safety data included in the discharge home summary letter should be sought to complete data collection.

If the discharge home coincides with the 36 weeks PMA visit, both assessments should be completed and recorded in the eCRF.

7.1.9 Clinical assessment at 24 months (± 3 months) corrected age

A further clinical assessment will be performed at 24 months (± 3 months) corrected age at the participating study centers. In this occasion, age and age corrected for prematurity will be collected. This clinical assessment will be based on:

- Bayley Scales of Infant Development Edition III or IV (see Section [7.2.4](#));
- Health status questionnaire (additional evaluation of growth and development, respiratory assessment);
- Vital signs (SBP, DBP, MBP, HR and RR);
- Body weight, length and OFC.

7.2 Investigations

7.2.1 Neonatal pain assessment by Premature Infant Pain Profile (PIPP) score [\[26\]](#)

This is a composite score system based on the following indicators:

- Gestational age;
- Behavioral state before painful stimulus;
- Change in heart rate during painful stimulus;
- Change in oxygen saturation during painful stimulus;
- Brow bulge during painful stimulus;
- Eye squeeze during painful stimulus;
- Nasolabial furrow during painful stimulus.

The interpretation can vary from a minimum score of 0 to a maximum score of 21. The higher the score the greater the pain behavior ([APPENDIX IV](#)).

7.2.2 Vital signs and Blood tests

- Heart rate and pre-ductal SpO₂ are measured by pulse oximetry;
- Respiratory rate is shown on the cardiorespiratory monitor and can be measured by bioimpedance electrode sensors or chest wall motion sensors;
- Systolic, diastolic and/or mean blood pressures are measured either in a non-invasive or in invasive way, depending on the availability of an arterial catheter;
- Blood gas analysis (values of pH, pCO₂, pO₂, HCO₃, BE, lactate) will be performed either with arterial or capillary samples. Small volumes of blood (e.g. some droplets) will be collected in pre-heparinized tubes or syringes. When collected through an arterial line, at least 1.6 ml of blood should be withdrawn before collection of the blood gas sample to avoid contamination errors.

7.2.3 Assessment of Bronchopulmonary Dysplasia

To define presence and severity of BPD, the definition from the National Institute of Child Health and Human Development (NICHD) will be used, with some adaptation [4] (Table 4). According to this definition, BPD is diagnosed if treatment with >21% oxygen is required for at least 28 days; for subjects with GA at birth <32 weeks (including our study population); severity of BPD is assessed at discharge or at 36 weeks PMA, whichever comes first, and is based on requirement of oxygen and/or positive pressure ventilation (Table 4). It is classified as mild, if at the time point of assessment the subject is breathing room air, moderate if still needs for supplemental oxygen less than 30%, severe if needs oxygen greater than or equal to 30% and/or positive pressure (PPV or nCPAP).

In this clinical study, BPD assessment will be performed at 36 weeks PMA for all treated subjects. If the discharge home is before the 36 weeks PMA and the subject is discharged with supplemental oxygen and/or positive pressure, a further visit will be required at 36 weeks PMA. If the discharge home is before 36 weeks PMA and the subject is discharged without supplemental oxygen or any respiratory support, an on-site visit is not mandatory, but the Investigator should contact the caring pediatrician to collect the relevant information and complete the evaluation.

Table 4

Definition of bronchopulmonary dysplasia for infants with GA at birth < 32 weeks:

Diagnostic criteria adapted from 2001 NICHD consensus workshop [4]

Gestational Age	< 32 wks
Time point of assessment*	36 wks PMA
Treatment with oxygen >21% for at least 28 days plus	
Mild BPD	Breathing room air
Moderate BPD	Need for <30% oxygen
Severe BPD	Need for ≥30% oxygen and/or positive pressure (PPV or NCPAP)

* Assessed at 36 weeks timepoint for all the study subjects when possible

7.2.4 Clinical assessment of growth and development and respiratory morbidity, using a health status questionnaire

The Clinical assessment of growth and development and respiratory morbidity will be done through a questionnaire to record weight, length and head circumference, result of the last cardiological evaluation and timing, the feeding method, the cerebral palsy, seizures, functional disability (vision, hearing, and communication), respiratory conditions and morbidity. This latter is mainly addressed to test the BPD severity (if any) at two-year corrected age.

To measure cognitive and language development, the score from the related sections of the Bayley Scales III and IV (i.e. cognitive and language domains) will be reported in the questionnaire. Bayley Scales of Infant Development is a standard series of measurements used primarily to assess the motor (fine and gross), language (receptive and expressive), and cognitive development of infants and toddlers, aged 0-3. This measure consists of a series of developmental play tasks and takes between 45 - 60 minutes to administer. Raw scores of successfully completed items are converted to scale scores and to composite scores. These scores (recorded in the eCRF) are used to determine the child's neurodevelopmental performance compared with norms taken from typically developing children of their age (in months).

8. EFFICACY ASSESSMENTS

The following variables will be used to describe the efficacy of the two procedures:

- Percentage of neonates needing invasive mechanical ventilation (MV) in the first 72 hours of life, 28 days PNA and within 36 weeks PMA defined as follows:

ETT group

- neonates not extubated within 1 hour from initial surfactant administration and receiving MV for more than 1 hour;
- neonates extubated and re-intubated to receive MV of any duration.

LISA group

- neonates intubated to receive MV of any duration,
 - Duration of invasive ventilation (hours) in the first 72 hours of life, 28 days PNA and within 36 weeks PMA;
 - Percentage of neonates needing any intubation procedure, outside the initial surfactant administration period, in the first 72 hours of life, in the first 28 days PNA and within 36 weeks PMA;
 - SpO₂ at time 0 (study treatment administration), 5, 15, 30 minutes, at 1, 6, 12, 24, 48, 72 and 120 hours post treatment; additionally, at 28 days PNA and at 36 weeks PMA for neonates still receiving any form of respiratory support;
 - FiO₂ at time 0 (study treatment administration), 5, 15, 30 minutes, at 1, 6, 12, 24, 48, 72 and 120 hours post treatment; additionally, at 28 days PNA and at 36 weeks PMA for neonates still receiving any form of respiratory

support;

- SpO₂/FiO₂ at time 0 (study treatment administration), 5, 15, 30 minutes, at 1, 6, 12, 24, 48, 72 and 120 hours post treatment; additionally, at 28 days PNA and at 36 weeks PMA for neonates still receiving any form of respiratory support;
- Percentage of neonates needing additional surfactant doses and number of surfactant doses;
- Duration of oxygen alone supplementation (days) and any non-invasive ventilation during the study (days);
- Blood gas analysis, specifically acid-base balance parameters (i.e. pH, pCO₂, pO₂, HCO₃, BE, lactate) pre-surfactant administration (when applicable), at 1 hour, 6 hours, 24, 48 and 72 hours after study treatment.

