Efficacy variables	
 • Percentage of neonates needing invasive mechanical ventilation in the first 72 hours of life, at 28 days PNA and within 36 weeks PMA • Duration of invasive ventilation (hours) in the first 72 hours of life, 28 days PNA and within 36 weeks PMA • Percentage of neonates needing any intubation procedure, outside of the initial surfactant administration period, in the first 72 hours of life, 28 days PNA and 36 weeks PMA • SpO₂ at time 0 (study treatment administration), 5, 15, 30 minutes, at 1, 6, 12, 24, 48, 72, and 120 hours post treatment; additionally, at 28 days PNA and at 36 weeks PMA for neonates still receiving any form of respiratory support • FiO₂ at time 0 (study treatment administration), 5, 15, 30 minutes, at 1, 6, 12, 24, 48, 72, and 120 hours post treatment; additionally, at 28 days PNA and 36 weeks PMA for neonates still receiving any form of respiratory support • SpO₂/FiO₂ at time 0 (study treatment administration), 5, 15, 30 minutes, at 1, 6, 12, 24, 48, 72, and 120 hours post treatment; additionally, at 28 days PNA and 36 weeks PMA for neonates still receiving any form of respiratory support • Percentage of neonates needing additional surfactant (Curosurf[®]) doses and number of surfactant doses • Duration of oxygen supplementation (days), any non-invasive ventilation during the study (days) • Blood gas analysis, specifically acid-base balance parameters (i.e. pH, pCO₂, pO₂, HCO₃, BE, lactate) pre-surfactant administration (when applicable), at 1 hour, 6 hours, 24, 48, 72 hours after study treatment

Safety Monitoring	
An Independent Safety Monitoring Board (ISMB) will provide ongoing trial review for the monitoring of subjects' safety. An ISMB meeting will be scheduled after the first 15 neonates have been enrolled. If no safety concerns are raised, enrollment will continue and will be extended to newborns with GA at birth between 25⁺⁰ weeks up to 28⁺⁶. Before obtaining a favorable opinion from the ISMB, only newborns with GA from 27⁺⁰ to 28⁺⁶ weeks will be enrolled. Further ISMB meetings will be scheduled after the first 60, 105 and 150 subjects, respectively. Ad-hoc ISMB meetings can be scheduled, if needed, in case of unexpected safety issues.

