	
 • Weight, OFC and length at discharge home or 40 weeks PMA will be summarized by treatment group by descriptive statistics. • Percentage of neonates needing invasive or non-invasive respiratory support at discharge home or 40 weeks PMA will be summarized by treatment group by frequency distribution • Neonates needing respiratory medications at discharge home or 40 weeks PMA will be summarized by treatment group by frequency distribution • Bayley Scales of Infant Development (BSID) (cognitive and language scores) will be summarized using descriptive statistics by treatment group and BSID version (III or IV). • Vital signs and all other variables collected through the questionnaire (i.e., anthropometric measures, cerebral palsy, seizures, feeding method, functional disability and respiratory morbidity) will be summarized by treatment group by frequency distribution or descriptive statistics as appropriate.
Statistical methods	Efficacy variables 
 • Percentage of neonates needing invasive mechanical ventilation in the first 72 hours of life, in the first 28 days PNA and within 36 weeks PMA will be compared between groups using the Cochran-Mantel-Haenszel (CMH) test adjusted for gestational age group. The CMH adjusted difference with its 95% confidence interval (CI) will be presented. Additional analysis will be performed to explore the impact of use of sedation and/or analgesia. • Duration of invasive mechanical ventilation in the first 72 hours of life, in the first 28 days PNA and within 36 weeks PMA will be compared between treatment groups by using the Mann-Whitney U-test. • Percentage of neonates needing any intubation procedure, outside the initial surfactant administration period, in the first 72 hours, in the first 28 days PNA and within 36 weeks PMA will be compared between treatment as need for invasive mechanical ventilation. • SpO₂ will be analysed using a linear mixed model for repeated measures (MMRM) including treatment, time point, treatment by time point interaction, and gestational age group as fixed effects and pre-procedure SpO₂ as covariate. The adjusted means in each treatment group, the adjusted mean difference between treatments and their 95% CIs at each time point and averaged over the first 120 hours post treatment will be estimated by the model. Time profile plot of mean SpO₂ in the first 120

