6.2.3.6 Additional surfactant treatment

Up to two repeated doses could be administered at 100 mg/kg.

A second surfactant dose (poractant alfa 100 mg/kg) will be administered using the same technique as the first dose administration in case of lack of efficacy, or clinical deterioration,

as per randomization criteria ($FiO_2 \geq 0.30$ to maintain preductal oxygen saturation (SpO_2) in the target range 88–95%), within approximately 12 hours from the initial dose.

After the first and the second surfactant administration, neonates could receive a third surfactant dose (poractant alfa 100 mg/kg). If a third dose is administered, it will be provided through a standard technique. Neonates could be intubated (LISA group) or re-intubated (control group) for MV at neonatologist's discretion, if one or more of the below detailed conditions for MV in section 6.2.3.7 are satisfied.

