6.3 Packaging

Chiesi Farmaceutici S.p.A. will supply the study medication for both groups as well as the thin catheter (CHF 6440) for the administration in the relevant LISA treatment group.

The study medication kit is composed of a single glass vials of 3 ml of Poractant alfa for initial dosing or possible re-dosing; the vial will be packed in an outer box and will be provided to

the investigational sites. Each vial is for single use only. Any need for dosing and re-dosing will require a vial to be issued via IRT (see Section [6.6](#)).

CHF 6440 catheters will be packed and provided separately.

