6.6 Treatment Code

The study medication (Poractant alfa) will be packaged and uniquely numbered. The IRT will be used to assign both initial and subsequent kits in order to have an inventory control and subject dosing tracking. The IRT will also maintain quantities, kit numbers, drug types, batch/code numbers, expiration dates and do not dispense after these dates. The IRT will monitor inventory levels at all sites and manage the study drug re-supply.

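### The any-intubation efficacy variable exempts only the first-dose intubation, so a second-dose re-intubation in the control arm counts as an event while catheter redosing in the LISA arm does not

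*Protocol*

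**What the plan says.** The Protocol Outline (efficacy variables) and Section 8 define the variable in near-identical words: "Percentage of neonates needing any intubation procedure, outside of the initial surfactant administration period" in the outline and "Percentage of neonates needing any intubation procedure, outside the initial surfactant administration period, in the first 72 hours of life" in Section 8. The windows are 72 hours of life, 28 days PNA and 36 weeks PMA. The outline's statistical methods say that it "will be compared between treatment as need for invasive mechanical ventilation", and Section 12.3.4 says the same. That means a CMH test adjusted for gestational age group, with the adjusted difference and its 95% CI.

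On redosing, Section 6.2.3.6 states: "A second surfactant dose (poractant alfa 100 mg/kg) will be administered using the same technique as the first dose administration", and places that dose "within approximately 12 hours from the initial dose". For a further dose it says: "If a third dose is administered, it will be provided through a standard technique".

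The phrase that sets the exempt period is not defined. Elsewhere, however, the protocol uses *initial* for the first dose as opposed to later ones. Examples are the timing in Section 6.2.3.6 just quoted, Section 6.6 ("The IRT will be used to assign both initial and subsequent kits") and the control-arm definition of mechanical ventilation (MV) in Section 8. Section 6.3 also separates dosing from redosing: "Any need for dosing and re-dosing will require a vial to be issued via IRT".

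**The concern.** By exempting the first dose, the variable already accepts that an intubation required by the assigned technique should not count as needing intubation. The second dose is given by the same assigned technique but has no exemption. Two neonates with the same respiratory course, redosed under the same rule, are then scored differently because of their allocation.

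The variable is listed under efficacy and worded as a need, and its difference is reported with a confidence interval. A reader will take a difference in favour of LISA as less respiratory failure after treatment. Some of it may only be the tube used for dose 2 in the control arm.

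**Working it through.** **Step 1. Follow a second dose through each arm.**

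| | Control | LISA |
|---|---|---|
| First dose (6.2.3.3, 6.2.3.4) | Endotracheal tube; exempt from the count | Thin catheter during NIV; no tube |
| After the first dose (6.2.3.4) | Extubated at once, or within one hour if put on the ventilator; back on NIV | Stays on NIV |
| Second dose (6.2.3.6) | Same technique, so normally a new intubation: **event** | Same technique, so catheter: **no event** |
| Third dose (6.2.3.6) | Standard technique | Standard technique |

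The asymmetry belongs to the second dose. The third uses the standard technique in both arms. A control neonate still intubated at dose 2, or also intubated later for another reason, adds nothing. Only neonates whose sole later intubation is for dose 2 matter.

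**Step 2. Timing.** The first dose is given by 24 hours after birth (Section 6.2.2) and the second within about 12 hours of it. 24 + 12 = about 36 hours, which is before 72 hours, so these events enter all three windows.

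**Step 3. Size fixed by the documents.** Section 12.1 plans 100 LISA and 50 control neonates. One such control neonate adds 1/50 = 2 percentage points to the control rate. The protocol states no event rate, effect size or power for this variable, so there is no figure of its own to reproduce.

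**Step 4. Illustration with assumed rates.** Let b be the share intubated for other reasons, equal in both arms. Let q be the share of otherwise non-intubated neonates who are redosed, with control neonates already extubated by then. Assume that no LISA catheter redosing fails.

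- LISA rate = b
- Control rate as written, c = b + (1 − b)q
- Shift = c − b = (1 − b)q
- 95% CI half-width (unstratified) = 1.96 × √[b(1 − b)/100 + c(1 − c)/50]

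Example with b = 0.20 and q = 0.20: c = 0.20 + 0.80 × 0.20 = 0.36, so the shift is 16 points, or 50 × 0.16 = 8 control neonates. The half-width is 1.96 × √(0.16/100 + 0.2304/50) = 1.96 × 0.0788 = 15.4 points.

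Each cell gives shift / half-width in percentage points:

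| | q = 5% | q = 10% | q = 20% |
|---|---|---|---|
| b = 20% | 4.0 / 14.2 | 8.0 / 14.7 | 16.0 / 15.4 |
| b = 30% | 3.5 / 15.9 | 7.0 / 16.1 | 14.0 / 16.4 |
| b = 40% | 3.0 / 16.7 | 6.0 / 16.8 | 12.0 / 16.9 |

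Relative to the half-width, the shift is about 0.2–0.3 at q = 5% and 0.7–1.0 at q = 20%. If b is higher in the later windows, it shrinks: at b = 60% it is 0.40 × q, that is 2, 4 and 8 points.

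**The case against.** **The count describes a real consequence of the assigned strategy.** The randomised strategies include the redosing technique, and Section 1.2 presents avoidance of intubation, even briefly, as the point of LISA. A control neonate re-intubated for dose 2 really is intubated again. This stands: a reader might infer that these events are misclassified, and the documents do not support that. The count is valid as procedure burden. What is missing is a label saying so, and a way to see how much of it is redosing.

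**Other variables cover respiratory need.** Need for MV has its own definition in Section 8, and redosing is compared by arm in Section 12.3.4. This stands in part. The redosing comparison does not identify neonates whose only later intubation was for dose 2, and it leaves out those with pulmonary hemorrhage. The MV definition does not say whether brief ventilation at a second dose counts.

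**The exempt period is undefined, and the SAP may settle it.** A reading that includes redosing is possible but goes against the protocol's own use of *initial*. Either way, one sentence is needed.

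**Events without respiratory failure.** A reader might infer that a control event can be scored with no MV criterion met, since Section 6.2.3.6 ties the second dose to FiO2 ≥ 0.30 while the oxygen criterion in Section 6.2.3.7 is ≥ 0.45. The documents do not settle this. The lead sentence of Section 6.2.3.7 also covers intubation for further surfactant doses, so which criteria govern a second-dose intubation is unclear.

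**Conclusion.** The asymmetry is in the text: a second-dose re-intubation is a control-arm event, and catheter redosing in the LISA arm has no counterpart to it. As written, part of any difference in favour of LISA can reflect the assigned redosing device.

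Only the 2 points per neonate come from the documents. The ranges of 3–4 points (q = 5%) and 12–16 points (q = 20%) rest on assumed rates, equal underlying need in both arms and no failed catheter redosing. A reader might infer that the comparison is likely to show a spurious LISA benefit. Without a redosing or intubation rate in the protocol, that cannot be said, and at low redosing rates the shift is well inside the confidence interval.

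Section 1.1 calls the study explorative, Section 12.1 defines no primary efficacy endpoint, and no decision rule uses this variable. This is a minor to moderate issue of interpretation.

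**What to change.** Change the endpoint wording and the analysis only:

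1. Keep the first-dose exemption as it stands. Do not attach a one-hour limit to it. Late first-dose extubations, almost all in control, would then become events and would duplicate the MV variable.
2. Keep the current count, and label it as including redosing intubations, that is, as procedure burden.
3. Add a companion count, compared by the same CMH method. It leaves out a control-arm intubation made to give the second dose by the assigned technique and ending in extubation within one hour of that dose. Identify these from the recorded intubation, dosing and extubation times. The one-hour limit follows the procedure definition in Section 10.8.
4. In the LISA arm, keep counting every endotracheal intubation, including one after failed catheter redosing, and show those separately so that a failure of the technique is not hidden.
5. State in the MV definition whether brief ventilation at a second dose counts as MV.
6. Reconcile Sections 6.2.3.6 and 6.2.3.7 on which criteria govern intubation for further doses. No clinical rule is proposed here.

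The cost is wording in the outline and in Sections 8 and 12.3.4, plus one extra table. Section 7.1.2 already collects dates and times of intubation and ventilation, and each redose needs a vial issued through the IRT. The time of the second dose must still be confirmed as an eCRF field, because the recorded criterion for intubation may not separate redosing from MV. The sponsor should also accept that the apparent LISA advantage may be smaller in the companion count.
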